Thus, the objective of this national quality improvement project is to develop an adaptive strategy to improve implementation of VA Risk ID to fidelity. Using a sequential multiple assignment randomized trial (SMART) design, two evidence-based implementation strategies will be evaluated: 1) Audit and Feedback (A/F); 2) A/F plus External Facilitation (A/F+EF). We will evaluate these strategies across several domains based on the RE-AIM OUEST mixed methods framework⁹. In addition to focusing on implementation outcomes, such as the impact of these strategies on implementation of VA Risk ID to fidelity, and potential barriers to adopting these strategies, we will also examine the impact of the clinical innovation (i.e., VA Risk ID) on patient-level outcomes. **Primary Aim:** Among sites that do not meet the benchmark for adequate performance (i.e., completion of secondary screening and CSRE for 80% or more of eligible patients) following 6 months of Implementation as Usual (IAU), does the addition of A/F for 10 months significantly improve scores on VA Risk ID performance measures compared to IAU alone? Secondary Aims: 1) Among sites that continue to not meet the benchmark for adequate implementation after 10 months of A/F, does the addition of EF significantly improve scores on VA Risk ID performance measures compared to A/F alone? 2) Among sites that meet the benchmark following A/F alone, is performance maintained following discontinuation of A/F? Outcomes for primary and secondary aims will use clinical performance measures extracted from VA's External Peer Review Program (EPRP) that reflect key practice elements of VA Risk ID: completion of the primary suicide screen, timely completion of the secondary suicide screen and timely completion of the CSRE. Exploratory Aims: 1) Examine the extent to which VA Risk ID is reaching the intended population and compare the characteristics of Veterans reached to all Veterans eligible for screening: 2) Examine contextual factors that may impact the a) implementation of VA Risk ID to fidelity and b) adoption of the implementation interventions. 3) Examine whether Veterans who receive the CSRE are more likely to receive a safety plan than Veterans who screen positive on the primary screen only. **This project directly**

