C1. Evaluation Framework. RE-AIM QUEST⁹ will provide an overarching framework for testing the impact of the proposed adaptive implementation strategy. RE-AIM QUEST expands RE-AIM by allowing investigators to understand not only whether Reach, Effectiveness, Adoption, Implementation and

Maintenance vary across sites and conditions, but also how and why these variations occur⁹. Moreover, RE-AIM was selected because of its ability to provide an approach to evaluation that focuses both on the impact of the implementation interventions and the impact of the clinical innovation (Table 1).

RE-AIM Domain	Operationalization	Data Sources			
Level of Evaluation: Clinical Innovation					
Reach	The absolute number and representativeness of Veterans that received the primary, secondary screens and CSRE.	Administrative (CDW) Data			
Effectiveness	Whether Veterans who receive the CSRE are more likely to receive a safety plan (SP) compared to Veterans who screen positive on the primary screen only.	Administrative (CDW) data			
Implementation	Percentage of eligible Veterans sampled at each facility who receive the different stages of VA Risk ID as intended; barriers & facilitators to implementation to fidelity.	EPRP measures			
Level of Evaluation	on: Implementation Strategy				
Effectiveness	Effect of A/F intervention on implementation of VA Risk ID to fidelity compared to IAU alone. Effect of A/F + EF intervention on implementation of VA Risk ID to fidelity compared to A/F alone.	EPRP measures			
Adoption	Number of sites randomized to the implementation interventions that participated. Characteristics of participating/non-participating sites and reasons for participating/not participating.	Key Informant (KI) & Debriefing Interviews			
Implementation	mplementation Percent of sampled instances of implementation intervention delivered to fidelity (i.e., met criteria for adherence).				
Maintenance	Maintenance of adequate implementation following removal of A/F; Sustained implementation of VA Risk ID for high performers	EPRP measures			

Table 1. Application of RE-AIM, Level of Evaluation, Operationalization, and Data Sources

^a All domains will be evaluated at Baseline, Post-Intervention Phase I and II except for maintenance, which will be evaluated at postintervention phase I and II

C2. Design. a. Primary and secondary aims (Effectiveness and Maintenance of the implementation

Figure 2. SMART Design and Intervention Phases

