C5. Randomization. **a. Primary Tailoring Variable (PTV):** The PTV determines the set of randomized intervention options. Thus, the PTV in any SMART must be a proximal measure of the outcome that denotes early success or failure and can be implemented in practice²⁸. In this SMART, the PTV is a predetermined benchmark for adequate implementation. This benchmark will be based on C-SSRS Screener fallouts and CSRE fallouts. The cut-off for both must be 80% or higher (i.e., less than 20% fallouts) to be considered adequate implementation. This cut-off was chosen with input from the program partner and previous QI projects with the program office that involved setting implementation benchmarks (i.e., REACH VET implementation). This benchmark is meant to represent a performance target that all facilities are expected to work towards. Preliminary data indicates that, across facilities since October 2018, the 1st quartile of C-SSRS fallouts is 47.9% (range: 12.9% - 87.4%), and the 1st quartile of the CSRE fallouts is 61.2% (range: 12.5% - 100%). 75% of sites currently have C-SSRS and CSRE fallout percentages greater than 47.9% and 61.2%, respectively. Based on these numbers at least 80-90% of sites currently do not meet criteria for adequate performance. We expect that this number to decrease some as implementation continues, but we expect that many sites will still have significant room for improvement when this project begins. The program partner may adjust this benchmark based on additional data gathered. **b.** Randomization procedures: Randomization will occur at the site level. VAMCs that are not meeting the benchmark for adequate implementation (See PVT above) at Baseline month 6 will be randomized 1:1 (R1) to receive A/F or continued IAU for 10 months. A/F sites that do not meet the benchmark for adequate implementation at the 10th interventional month will be randomized 1:1 (**R2**) to either continue A/F or augmentation with EF (A/F + EF) for an additional 10 months. A/F sites that meet the criteria for adequate implementation will be randomized 1:1 (**R3**) to either continue A/F or discontinue A/F and return to IAU. R1 will be stratified by facility complexity level (i.e., high, medium and low) and level of performance (i.e., low or moderate) at baseline. The Facility Complexity Model²⁹ classifies VA medical facilities at levels 1a, 1b, 1c, 2, or 3. Level-1a facilities are the most complex and level-3 facilities are the least complex. Levels 1a-1c will be considered high complexity, level 2- medium complexity and level 3- low complexity. Approximately 61% of facilities (N=85) are high complexity, 17% (N=24) are moderate and 22% (N=31) are low complexity. Additionally, the average of the C-SSRS Screener and CSRE fallout rates for the 6th Baseline month will be calculated for each facility to be randomized (R1) and the median of these averages will be used to determine stratification by level of performance (i.e., low – above median fallout rate, or moderate – below median fallout rate). R2 will also be stratified by facility complexity level and level of performance (based on the median of the fallout rate at the 10th month of phase 1). R3 will be stratified only by facility complexity level as all sites will have met the benchmark. These procedures will ensure that intervention groups are balanced for site variables that may correlate highly with outcomes. If less than 12 sites will be randomized at R2, stratification will only occur based on facility complexity, unless all facilities are at the same level of complexity in which case only median level of performance will be used for stratification.

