EPRP outcomes of change in sui2 and csra1 from the 6th month of the baseline period to the 10th month of the first interventional phase will each be modeled as a function of group (A/F vs. IAU), the baseline outcome value, the stratification variables of facility complexity (high, medium, low) and baseline performance level (above or below the median average fallout rate), and geographic region (West, Midwest, Southwest, Southeast and Northeast). Inference will be made based on the coefficient associated with the group variable and 97.5% confidence intervals (CI) will be reported (alpha=0.025). A similar analysis will be used to determine the effect of A/F on the change in the EPRP outcome for the primary screeners (sui40 and sui51), with 95% CIs reported. **c.** Secondary Aims: 1). To test the effect of the addition of EF for those who do not implement adequately at end of interventional phase 1, the primary EPRP outcomes of change in sui2 and csra1 from the 10th month of interventional phase 1 (baseline for interventional phase 2) to the 10th month of interventional phase 2 will be modeled as a function of group, the baseline outcome value, the stratification variables and geographic region (if sample sizes allow for control of this variable). Inference will be made based on the coefficient associated with the group variable and 95% CIs will be reported. A similar analysis will be used to determine the effect of the addition of EF on the change in the EPRP outcome for the primary screeners (sui40, sui51), with 95% CIs reported. 2). An analysis similar to that described for secondary aim 1 will be employed to investigate the effect of discontinuing A/F for those who implemented adequately at the end of interventional phase 1. Lastly, we will use a data driven approach to characterize each of the four EPRP outcomes over time for each group outlined in Figure 2 (group 1-6). Mixed effects models with a random intercept and slope will be used to model each of the four EPRP outcomes as a function of categorical group (1-6) and an interaction between group and a Bspline transformation on time (allowing the outcome to vary smoothly over time, using 21-time points, i.e., the 6th baseline month and every month of each interventional phase) such that each group will have its own trajectory. The trajectory for each group will be plotted with pointwise confidence intervals. **d. Exploratory** Aims: *i. Reach*: Reach will be calculated using the following formula: actual number of Veterans screened or evaluated/ actual number of Veterans eligible for screening, calculated cumulatively across all three study phases and all sites. We will calculate reach for each assessment stage of VA Risk ID. We will examine representativeness of patients reached by comparing demographic characteristics and other relevant variables (e.g., settings in which screening was completed) between eligible Veterans who were screened and/or evaluated and those who were not. Given that Veterans are clustered within facility, if the intra-class correlation between Veterans within each facility is estimated to be greater than zero, methods appropriate for clustered data will be employed to compare the variables of interest. For continuous variables, linear mixed models will be used with a random facility effect and non-normal data will be transformed. For binary variables, generalized linear mixed models will be used with a logit link and for categorical variables, random effects multinomial models will be employed. If the ICC is zero, t-tests, Wilcoxon rank-sum, Chi-square or Fisher's exact tests will be used, as appropriate. *ii. Adoption & Implementation Factors:* Key informant interviews will be used to examine factors influencing adoption of the implementation interventions and barriers and facilitators of implementing VA Risk ID to fidelity. All qualitative data sources, including interview transcripts and documents will be compiled and managed using Nvivo V. 9.0 software. We will take a general inductive approach³⁴. Specifically, data analysis will be determined by both the research objectives (i.e., domains of the RE-AIM framework) and multiple readings and interpretation of the raw data (i.e., content analysis). The goal is to establish clear links between the research objectives and the summary findings derived from the raw data. *iii. Effectiveness- Clinical Innovation:* We wish to examine whether Veterans who receive the CSRE are more likely to receive a safety plan within 2 weeks than those who screen positive on the primary screen only. To account for clustering of Veterans within facility, a mixed-effects logistic regression will be used to model the outcome of safety plan within 2 weeks (yes/no) as a function of group (receipt of CSRE/positive on primary screen only) with a random subject within facility effect. Additionally, to determine if receipt of a timely safety plan depends on whether Veterans are considered to be at low, moderate or high acute risk of suicide, this model will be repeated with the addition of a group by (categorical) acute risk interaction. Odds ratios for receipt of CSRE relative to positive on primary screen only will be reported for each level of acute risk with 95% confidence intervals.

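### The random-facility models planned for representativeness of reach understate disparity between facilities, most where each facility contributes many Veterans

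*Protocol*

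**What the plan says.** The Specific Aims set Exploratory Aim 1 as a comparison across the whole system: to "compare the characteristics of Veterans reached to all Veterans eligible for screening". Table 1 in Protocol C1 defines the Reach domain as "The absolute number and representativeness of Veterans that received the primary, secondary screens and CSRE". In C7 d.i the reach proportion is pooled, being "calculated cumulatively across all three study phases and all sites", and is worked out separately for each stage of VA Risk ID.

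Representativeness is then tested by comparing demographic and other variables ("e.g., settings in which screening was completed) between eligible Veterans who were screened and/or evaluated and those who were not"). The method depends on the ICC: "if the intra-class correlation between Veterans within each facility is estimated to be greater than zero, methods appropriate for clustered data will be employed". For continuous variables: "For continuous variables, linear mixed models will be used with a random facility effect and non-normal data will be transformed". Binary variables get a logit mixed model and categorical variables a random-effects multinomial model. Ordinary two-group tests are kept only for an ICC of zero.

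The SAP covers the primary and secondary aims. It says nothing about reach.

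**The concern.** The question is marginal: among all eligible Veterans, do those reached differ from those not reached? A random facility effect changes the comparison as well as the standard error. The coefficient on screened status becomes a weighted mix of the within-facility and between-facility contrasts. The weight on the between-facility part falls as the number of Veterans per facility rises. If a group is missed mainly because it attends facilities that screen few people, that is a between-facility difference, and the model assigns most of it to the facility effects.

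The ICC rule does not protect against this. Marginal tests are used only when the ICC is zero. Facilities then do not differ in mix, and the two answers coincide anyway. When the answers can differ, the plan uses the model that shrinks the difference. At stake is whether the programme office learns that a group is under-reached because of where it receives care.

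A smaller issue concerns one named comparison variable, the setting in which the screen was completed. It has no value for a Veteran who never had the primary screen.

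**Working it through.** The plan states no figure for this analysis, so there is none to reproduce. The check asks how much of a purely between-facility gap the planned model keeps.

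**Inputs from the documents**
- Up to 140 facilities (C2, C4).
- C-SSRS fallout from 12.9% to 87.4% across facilities (C5 a), so completion from 12.6% to 87.1%. CSRE fallout runs from 12.5% to 100%. No spread is given for the primary screen.
- The cohort is about 76.2% of Veterans in VHA care (Background). No count per facility is given.

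**Assumptions (not in the documents)**
- Facility completion q is uniform on 0.126 to 0.871.
- A binary characteristic has overall share 30% and facility SD τ = 0.10 (0.05 as the alternative).
- The correlation between facility share and q is -0.5.
- There is no disparity inside any facility.
- n Veterans per facility is 50, 200 or 2000.

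**Formulae** (linear mixed model, large-sample approximation; gaps shown as absolute values)
- Var(q) = 0.745²/12 = 0.0463, SD 0.215; mean q = 0.4985; mean q × (1 − mean q) = 0.250.
- Between-facility covariance C = 0.5 × 0.10 × 0.215 = 0.01075.
- Pooled gap = C/0.250 = 0.043, about 4 points.
- Average within-facility variance of screened status: 0.250 − 0.0463 = 0.2037.
- Residual variance s² = 0.30 × 0.70 − 0.01 = 0.20.
- Weight on between-facility information w = 1/(1 + nτ²/s²).
- Model coefficient = wC/(0.2037 + w × 0.0463).

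**Results, τ = 0.10**

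| n per facility | w | Coefficient | Share of the 4.3-point gap kept |
|---|---|---|---|
| 50 | 1/3.5 = 0.286 | 0.0142 (1.4 points) | 33% |
| 200 | 1/11 = 0.091 | 0.0047 (0.5 points) | 11% |
| 2000 | 1/101 = 0.010 | 0.0005 (0.05 points) | 1% |

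Another evaluation of the same type of set-up gave about 1.4, 0.6 and 0.1 points, so the values at 200 and 2000 are approximate.

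**Results, τ = 0.05.** Here s² = 0.21 − 0.0025 = 0.2075, C = 0.00538 and the pooled gap is 2.15 points. The weights are 0.624, 0.293 and 0.040. The model keeps 67%, 34% and 5% of the gap at n = 50, 200 and 2000. Smaller differences in mix therefore mean a smaller gap and less shrinkage.

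**Logit model.** A separate simulation fitted the planned logistic mixed model. It assumed a group share near 20%, a facility SD of 0.6 on the logit scale, facility reach from 12.9% to 87.4%, no within-facility disparity, and 20 replicates per setting.
- Correlation of size 1: the share of the marginal log odds ratio kept was 81% at 10 Veterans per facility, 39% at 50, 9% at 200, 2% at 1000 and 0.4% at 5000. At 5000 the marginal odds ratio was 0.61 and the model's 0.998.
- Correlation of size 0.5, 5000 per facility: marginal 0.785, model 0.999.

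**Setting variable.** At the primary stage an unscreened Veteran has no completion setting. Veterans eligible for the secondary screen or the CSRE have already had an earlier screen, so a setting exists in both groups, although C7 does not say that this is the one meant.

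**The case against.** The strongest reply is that the documents do not show the two conditions together. Near-complete loss of the gap needs large clusters, which are plausible for the primary screen. The only documented spread between facilities is for C-SSRS and CSRE fallouts, which arise after a positive screen and so rest on smaller denominators. That spread is also an early snapshot, which C5 expects to improve. No rural share or other patient mix is given by facility, and no correlation of mix with reach. The calculations impose zero disparity within facilities, so a coefficient near zero in large clusters is built in. The aim is exploratory, and raw percentages by group, if tabulated, would show the gap.

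Most of this stands, and it limits the size of the claim. A reader might infer that groups missed because their facility screens poorly will always look fully represented. The documents do not support that: a random-intercept model is not purely within-facility, and a material share of the gap can survive at 50 to 200 Veterans per facility. Nor do they show that any particular group is in fact under-reached, or that the setting comparison fails at every stage.

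What the reply does not remove is the mismatch. The aim is system-wide, the specified model down-weights the between-facility part, and the plan does not commit to reporting the raw comparison.

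**Conclusion.** The concern holds in a limited form. The planned models understate disparity that arises because some facilities reach fewer Veterans. In the linear-model illustration about 5% or less of such a gap survives at 2000 Veterans per facility. Between about a tenth and two thirds survives at 50 to 200, depending on how much facilities differ in mix. The first range plausibly describes the primary screen and the second the secondary screen and CSRE, but cluster sizes are an assumption throughout, and so are the facility SD, the group share and the correlation. Disparity within facilities is still detected.

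The primary and secondary aims are untouched. C3 names reach as the fallback primary outcome if validation of the EPRP measures fails. A reader might think that fallback is affected too, but it concerns the reach proportion and not this test. This is a worthwhile, low-cost correction to an exploratory analysis.

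**What to change.** In C7 d.i:

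1. Make the main representativeness result the pooled difference in means or proportions between reached and unreached Veterans, or equivalently reach by subgroup. Give confidence intervals from a facility-cluster-robust variance or a facility bootstrap, whatever the estimated ICC.
2. Report beside it the mixed-model estimate, or a model that adds the facility screening rate as a covariate, labelled as the within-facility component. The two together show whether under-reach arises inside facilities or between them.
3. For the primary screen only, replace the setting of completion with the setting of the visit at which the screen was due, which exists for both groups. For later stages, state which earlier screen's setting is used.

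The work uses the same CDW data. The cost is a change of wording, a little more analysis, and wider confidence intervals for the marginal comparison.
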